7.1.5.3. Dose Modification Guidelines for Temozolomide and Pamiparib

As outlined in [Sections 1.2.3, 1.3.1, 1.3.2, and 1.3.4](#), and discussed in [Section 1.5](#), PARP inhibitors, including pamiparib, show at least partial overlap with the safety profile of TMZ. Therefore, patients in Arms B and C of this study may experience AEs typical for these two drug classes at a higher frequency and/or severity. In addition, patients may encounter AEs that are uniquely caused by the novel combination of pamiparib and TMZ.

As outlined in [Section 1.2.3](#), TMZ is considered a treatment option but not a strongly established standard of care for the patient populations of this study. In the context of this study, the role of TMZ is to sensitize GBM cells to pamiparib through DNA damage that can be caused by relatively low doses of TMZ. Given these considerations, the decision to hold study drugs will always be made for both pamiparib and TMZ combined.

Given the favorable safety profile of pamiparib ([Sections 1.3.4 and 1.5](#)), it is reasonable to assume that a Grade 3 or 4 AE is more likely to be due to the addition of TMZ to pamiparib rather than pamiparib on its own. Following this rationale, the decision of a dose reduction will affect TMZ first, and a maximum of 2 TMZ dose reductions will be allowed. Should TMZ dose reduction in itself be insufficient to ensure tolerability of the combination regimen, dose reductions of pamiparib in 20 mg increments may be discussed with the medical monitor, and a maximum of 2 pamiparib dose reductions is allowed. Depending on the toxicity that is triggering a second TMZ dose reduction, the possibility of a concurrent pamiparib dose reduction should be discussed with the medical monitor. A patient must discontinue treatment with pamiparib and TMZ, if, after treatment is resumed at a lower dose, the toxicity recurs with the same or worse severity. Dose levels for TMZ and pamiparib are summarized in [Table 3](#).

Table 3: Individual Dose Levels for Temozolomide and Pamiparib

Dose level	Temozolomide (TMZ) ¹		Dose level	Pamiparib ²	
	Flat dosing QD	Dose equivalent		BID	QD
-1	20 mg	12 mg/m²	-2	20 mg	40 mg
1	40 mg	23 mg/m²	-1	40 mg	80 mg
2	80 mg	46 mg/m²	1	60 mg	120 mg
3	120 mg	69 mg/m²			
4	TBD	-			

Note: TMZ will be dose-reduced first for a maximum of 2 dose reductions. After discussions with the medical monitor, pamiparib may be dose-reduced next for a maximum of 2 dose reductions. Depending on the toxicity that is triggering a second TMZ dose reduction, the possibility of a concurrent pamiparib dose reduction should be discussed with the medical monitor. Once a dose of pamiparib or TMZ has been reduced, re-escalation is not allowed.

BID = twice daily; QD = once daily; TBD = to be determined

¹ Flat dosing of TMZ is used in this study. Dose equivalent information is provided for reference only and assumes an average body surface area of 1.73 m². The starting dose for Arm C is dose level 1. For Arm B, the first dose level of TMZ will be lower than or equal to a dose that has been determined to be safe and tolerable in Arm C.

² The dose for pamiparib used in this study is 60 mg BID. A QD schedule may be explored as outlined in [Section 4.2.1](#).

TMZ and pamiparib will be dose-modified as outlined in [Table 4](#). The hold and discontinue guidelines also apply to pamiparib (without TMZ) in Arm A. After a toxicity has adequately resolved, the decision in Arm A of resuming pamiparib treatment at the same dose level versus dose-reducing pamiparib should be made in discussion with the Medial Monitor.

Table 4: Criteria for Modification of Pamiparib and Temozolomide Dosing

Toxicity	Recommended Dose Modification
Hematologic	
Anemia (hemoglobin, Hb)	
Grade 2 (Hb < 10 - 8 g/dL)	First occurrence: continue dosing at current dose level Second and subsequent occurrences: hold pamiparib and TMZ until resolved to ≤ Grade 1 or baseline 
 • If resolved ≤ 14 days, then maintain dose levels • If resolved > 14 days, then ↓ TMZ by 1 dose level and continue pamiparib at same dose
Grade 3 (Hb < 8 g/dL)	Hold pamiparib and TMZ until resolved to Grade ≤1 or baseline 
 • If resolved ≤7 days, then maintain dose levels • If resolved >7 days, then ↓ TMZ by 1 dose level
Grade 4 (life-threatening consequences; urgent intervention indicated)	Hold pamiparib and TMZ until resolved to Grade ≤1 or baseline and ↓ TMZ by 1 dose level
Neutropenia (absolute neutrophil count, ANC)	
Grade 3 (ANC <1.0 - 0.5 x 10 ⁹ /L)	Hold pamiparib and TMZ until resolved to Grade ≤2 or baseline 
 • If resolved ≤7 days, then maintain dose levels • If resolved >7 days, then ↓ TMZ by 1 dose level
Grade 4 (ANC <0.5 x 10 ⁹ /L)	Hold pamiparib and TMZ until resolved to Grade ≤1 or baseline and ↓ TMZ by 1 dose level
Febrile neutropenia (ANC <1.0 x 10 ⁹ /L with single temperature of >38.3°C or sustained temperature of ≥38°C for >1 hour)	Hold pamiparib and TMZ until resolved and ↓ TMZ by 1 dose level
Thrombocytopenia (platelet count, PLT)	
Grade 3 (PLT <50 - 25 x 10 ⁹ /L)	Hold pamiparib and TMZ until resolved to Grade ≤1 or baseline 
 • If resolved ≤7 days, then maintain dose levels • If resolved >7 days, then ↓ TMZ by 1 dose level
Grade 4 (PLT <25 x 10 ⁹ /L)	Hold pamiparib and TMZ until resolved to Grade ≤1 or baseline and ↓ TMZ by 1 dose level

Table 4: Criteria for Modification of Pamiparib and Temozolomide Dosing (Continued)

Toxicity	Recommended Dose Modification
Renal	
Serum creatinine	
2-3 x ULN	Hold pamiparib and TMZ until resolved to Grade \leq 1 or baseline 
 • If resolved \leq7 days, then maintain dose levels • If resolved $>$7 days, then \downarrow TMZ by 1 dose level
Grade 3 ($>$ 3.0 - 6.0 x ULN) and Grade 4 ($>$ 6.0 x ULN)	Permanently discontinue pamiparib and TMZ
Hepatic	
Bilirubin	
Grade 2 ($>$ 1.5 - 3.0 x ULN) and Grade 3 ($>$ 3.0 - 10.0 x ULN)	Hold pamiparib and TMZ until resolved to Grade \leq 1 or baseline 
 • If resolved \leq7 days, then maintain dose levels • If resolved $>$7 days, then \downarrow TMZ by 1 dose level
Grade 4 ($>$ 10.0 x ULN)	Permanently discontinue pamiparib and TMZ NOTE: If Grade 3 or 4 hyperbilirubinemia is due to the indirect (unconjugated) component only, and hemolysis as the etiology has been ruled out as per institutional guidelines (eg review of peripheral blood smear and haptoglobin determination), then \downarrow TMZ by 1 dose level and continue treatment at the discretion of the investigator
AST and/or ALT	
Grade 3 ($>$ 5 and \leq 20 x ULN)	Hold pamiparib and TMZ until AST and/or ALT resolved to \leq 5 x ULN or baseline 
 • If \leq5 x ULN within 14 days, then \downarrow pamiparib and TMZ by 1 dose level • If second episode, permanently discontinue pamiparib and TMZ • If persistent for $>$14 days, permanently discontinue pamiparib and TMZ
Grade 4 ($>$ 20 x ULN)	Permanently discontinue pamiparib and TMZ

Table 4: Criteria for Modification of Pamiparib and Temozolomide Dosing (Continued)

Toxicity	Recommended Dose Modification
Pancreatic	
Pancreatitis Grade 3 or 4	Permanently discontinue pamiparib and TMZ
Cardiac	
Cardiac - Prolonged QTc interval QTcF >500 msec or >60 msec from the higher of the baseline or predose value	
 • Obtain triplicate ECGs (5 minutes apart) ~1 hour after initial ECG • If mean QTcF >500 ms or >60 msec from baseline value, hold pamiparib and TMZ until evaluation of ECGs by cardiologist 
 • Cardiology evaluation as soon as practical but within 7 days of initial abnormal ECG • If mean QTcF >500 ms or >60 msec from baseline value confirmed by cardiologist, permanently discontinue pamiparib and TMZ
Cardiac - general Grade 3	Hold pamiparib and TMZ until resolved to Grade ≤1 or baseline and ↓ TMZ 1 dose level
Grade 4	Permanently discontinue pamiparib and TMZ
Other adverse events	
Grade 3	Hold pamiparib and TMZ until resolved to Grade ≤1 or baseline and ↓ TMZ by 1 dose level No dose reduction required for asymptomatic laboratory abnormalities
Grade 4	Permanently discontinue pamiparib and TMZ

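### Table 4's hepatic rows need reconciling: the Grade 3 AST/ALT row lowers pamiparib together with TMZ although the text lowers TMZ first, and the unconjugated-bilirubin note leaves out Grade 2

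*Protocol*

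**What the plan says.** **Order of reduction.** The text of Protocol 7.1.5.3 states that "the decision of a dose reduction will affect TMZ first, and a maximum of 2 TMZ dose reductions will be allowed". The note under Table 3 repeats it: "TMZ will be dose-reduced first for a maximum of 2 dose reductions", with pamiparib next, after discussion with the medical monitor. The Dose Modifications note in the synopsis says the same. Where a toxicity triggers a second TMZ reduction, "the possibility of a concurrent pamiparib dose reduction should be discussed with the medical monitor". No other concurrent pamiparib reduction is raised in these places.

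**Table 4, AST/ALT Grade 3.** Both drugs are held until values are at 5 x ULN or less, or baseline. If 5 x ULN or less is reached within 14 days, the action is to lower "pamiparib and TMZ by 1 dose level". Persistence beyond 14 days means permanent discontinuation of both drugs, and so does recurrence: "If second episode, permanently discontinue pamiparib and TMZ".

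**Table 4, bilirubin.** Grades 2 and 3 share one instruction, "Hold pamiparib and TMZ until resolved to Grade" 1 or less, or baseline. Dose levels are kept if this takes 7 days or less; otherwise TMZ goes down one level. Grade 4 means permanent discontinuation. A NOTE then makes an exemption: "If Grade 3 or 4 hyperbilirubinemia is due to the indirect (unconjugated) component only, and hemolysis as the etiology has been ruled out", TMZ is lowered "by 1 dose level and continue treatment at the discretion of the investigator".

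**General rules.** Section 7.1.5.1 bars re-escalation of either drug. It also presents these as suggested guidelines that the investigator may modify.

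**The concern.** For AST/ALT, the same laboratory result leads to two different pamiparib doses depending on whether a site follows the table row or the text and notes. The choice cannot be undone later, because re-escalation is not allowed.

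For bilirubin, the exemption begins at Grade 3. An unconjugated Grade 2 rise has no matching provision, so the milder finding carries a mandatory-sounding interruption that the more severe one can avoid.

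At stake is consistent dosing across sites. Dose intensity of each component is part of a Phase 1b primary endpoint and a Phase 2 secondary endpoint (Protocol 3.1 and 3.2). SAP 6.5.1 summarizes reductions, interruptions and relative dose intensity. If sites followed different instructions, those summaries would mix tolerability with differences in how the document was read.

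**Working it through.** The plan gives no figure to reproduce here. The check sets the passages side by side, with one small calculation.

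**1. AST/ALT, first Grade 3 episode recovering within 14 days, patient on both drugs**

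Inputs: Table 3 gives pamiparib level 1 as 60 mg BID and level -1 as 40 mg BID. Assume no earlier reduction of either drug.

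- Table 4: TMZ down one level, pamiparib down one level. Change in pamiparib = (60 - 40)/60 = 33%.
- Text, Table 3 note and synopsis note: TMZ down one level, pamiparib unchanged. Change in pamiparib = 0%.

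TMZ falls by one level on both readings, so only pamiparib differs. SAP 6.5.1 defines relative dose intensity as actual over planned dose. For the days after the reduction, pamiparib therefore contributes 40/60 = 67% on one reading and 100% on the other.

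Could the passages already agree? The row's two-drug reduction can follow only a first AST/ALT episode, since a second means discontinuation. The text allows a concurrent pamiparib reduction only when TMZ is being reduced for the second time, and then only as a matter for discussion. The two coincide only if an earlier toxicity had already used one TMZ reduction and the discussion ended in a concurrent pamiparib cut. Going through the rest of Table 4, every other reduction is of TMZ alone, and the Grade 2 anemia row explicitly keeps the pamiparib dose. The AST/ALT row is the only one that lowers pamiparib.

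**2. Bilirubin, unconjugated component only, hemolysis ruled out**

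| Grade (x ULN) | Row | NOTE |
|---|---|---|
| 2 (>1.5 to 3.0) | Hold both; levels kept if resolved in 7 days or less, otherwise TMZ down one level | Not mentioned |
| 3 (>3.0 to 10.0) | Same hold | TMZ down one level, continue at discretion |
| 4 (>10.0) | Permanent discontinuation | TMZ down one level, continue at discretion |

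Read literally, 2.9 x ULN interrupts both drugs, while 3.1 x ULN, or a value above 10 x ULN, need not. The inversion concerns interruption. On dose level the order is mixed: a Grade 2 rise that resolves within 7 days loses no level, one that resolves later loses one TMZ level in addition to the hold, and the NOTE always costs one TMZ level. The NOTE also does not say whether it replaces the Grade 3 hold or only follows it.

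**The case against.** **The row may be a deliberate, specific exception.** Section 7.1.5.3 says both drugs are modified as set out in Table 4, and TMZ-first is introduced as a general rationale. A toxicity-specific row overriding a general default is a plausible reading. But no order of precedence is stated, and the TMZ-first note stands close to the pointer to Table 4. The conflict is softened, not settled.

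**The guidelines are flexible.** They are suggested, the investigator may depart from them, and changes should be discussed with the medical monitor beforehand if feasible. That central contact limits divergence but does not tell two sites which instruction is the starting point.

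**Grade 2 is only a temporary hold.** This is correct. The option to end a hold at baseline also helps some patients with raised starting values, since those with Gilbert's syndrome may enrol at up to 4 x ULN. Neither point says what the NOTE means for Grade 2.

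**Arm A during RT is not affected by the AST/ALT conflict.** Only the hold and discontinue guidelines carry over there, and resumption at the same or a lower dose is decided with the medical monitor. This stands, and the point is limited to patients receiving both drugs.

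**A stronger reading to avoid.** A reader might infer that the bilirubin gap distorts the DLT-evaluable set, with the milder case dropping out under the 70% dosing rule while the NOTE keeps the worse case in. The documents do not support this. Protocol 4.2.4 makes pamiparib-related Grade 3 or higher total bilirubin a DLT, with no unconjugated exemption. Protocol 11.2.1 and SAP 6.1 keep every patient with a DLT evaluable whatever dose was received, and Protocol 4.2.3 replaces non-evaluable patients where needed. Nor is there a hold-length threshold to be read from pamiparib alone. In Arm C the 70% rule also covers TMZ, which is given on Days 1 to 21: a 7-day hold in that span leaves TMZ at 14/21 = 66.7% while pamiparib is still at 21/28 = 75%.

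**Conclusion.** The point holds as a minor matter of wording. The AST/ALT row conflicts with three other statements in the protocol. For a patient on both drugs with no earlier reduction, the difference is 33% of the pamiparib dose from the first reduction onward against none at that step. The bilirubin part is a gap rather than a contradiction between two rules: the NOTE is silent on Grade 2 and on whether it displaces the hold, so on a literal reading interruption does not follow severity.

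The AST/ALT reduction is not immediate. It comes on resumption after a hold, and only with recovery within 14 days. The documents give no frequency for either event, so the number of patients affected cannot be estimated. Sample size, power and the efficacy analysis are untouched; the consequence is confined to consistent dosing and to descriptive summaries of reductions, interruptions and dose intensity.

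**What to change.** Reconcile the synopsis note, the text of 7.1.5.3, the Table 3 note and Table 4:

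- Make the Grade 3 AST/ALT row and the TMZ-first statements give the same instruction, or name the row as an explicit exception in each place.
- State whether the unconjugated-bilirubin NOTE applies to Grade 2, and whether it replaces the hold.

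Which clinical rule applies is for the sponsor's clinical team. The cost is amendment wording, with no effect on data collection or sample size. SAP Section 5 already reports 116 patients enrolled, so an amendment can help only those still on treatment. For the others, the study report can state which reading was applied when presenting the exposure summaries.

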7.1.6. Compliance and Accountability

Compliance will be assessed by the investigator and/or study personnel at each patient visit and information provided by the patient.

The investigator and/or study personnel is responsible for pamiparib accountability, reconciliation, and record maintenance. In accordance with all applicable regulatory requirements, the investigator or designated study center personnel must maintain pamiparib drug accountability records throughout the course of the study. This person(s) will document the amount of pamiparib received from the sponsor, the amount supplied and/or administered to and returned by patients, if applicable.

7.1.7. Disposal and Destruction

After completion of the study, all unused pamiparib will be inventoried and packaged for return shipment by the hospital unit pharmacist or other designated study personnel. The inventoried supplies will be returned to the sponsor or destroyed on site, after receiving written sponsor approval.

All unused TMZ will be destroyed on site according to regulations and local guidelines.

7.1.8. Treatment of Overdose from Study Drugs

Patients with a suspected overdose should be managed with appropriate supportive therapy as determined by the investigator in consultation with the medical monitor. Any AEs occurring because of an overdose should be reported to the medical monitor as well as being included in standard AE reporting.

7.1.9. Occupational Safety

Pamiparib is not expected to pose significant occupational safety risk to the study center personnel under normal conditions of use and administration. A material safety data sheet describing occupational hazards and recommended handling precautions will be provided to the investigator, where this is required by local laws, or is available upon request from the sponsor.

7.2. Concomitant Medications and Non-Drug Therapies

7.2.1. Permitted Medications and Supportive Care

All treatments and supportive care, including glucocorticoids, antiemetic therapy, hematopoietic growth factors and/or red blood cell/platelet transfusions, that the investigator considers necessary for a patient's welfare may be administered at the discretion of the investigator in keeping with the local standards of medical care. All concomitant medications taken during the study will be recorded on the case report form (CRF) including all prescription and over-the-counter (OTC) drugs, herbal supplements, and IV medications and fluids. If changes occur during the study period, documentation of that change in drug dosage, frequency, route, and date will also be included on the CRF.

All concomitant medications taken by or administered to the patient within 28 days before Day 1 and 30 days after the last day of study treatment should be recorded.

The eCRF entry must include the dose, regimen, route, indication, and start and stop dates of use of the prior and concomitant medications.

7.2.2. *Pneumocystis jirovecii* Pneumonia Prophylaxis

Glioblastoma patients receiving concomitant chemoradiotherapy with TMZ 75 mg/m² during 6 to 7 weeks or dose-dense TMZ regimens especially in combination with chronic use of corticosteroids have a high risk for developing *Pneumocystis jirovecii* pneumonia (previously known as *Pneumocystis carinii*).

For that reason, all patients in Arms B and C are required to receive *Pneumocystis jirovecii* pneumonia prophylaxis as per the package insert for TMZ. The choice of prophylactic medications will be left to the discretion of the investigator.

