4.1.1. Dose Escalation Phase (Phase 1b)

The Phase 1b, dose escalation phase consists of the following:

Arm A: Pamiparib (60 mg BID) administered continuously at increasing exposures of 2, 4, and 6 weeks in combination with RT administered for 6 to 7 weeks.

Arm B: Depending on the safety of the Arm A combination, the following combination may be explored: pamiparib (at the exposure determined as safe in Arm A) in combination with RT administered for 6 to 7 weeks and increasing doses of TMZ ([Section 4.2.1](#)).

In both Arms A and B, after RT is completed, patients will receive no further RT.

Maintenance Treatment for Arms A and B

Following completion of RT, at the discretion of the investigator and after discussion with the medical monitor, patients in the Arm A escalation and expansion and patients in Arm B escalation phases of the study may continue to receive pamiparib in combination with TMZ. TMZ will be given at a dose level lower than or equal to a dose that has been determined to be safe and tolerable in Arm C of study.

In the Arm B expansion phase of the study, maintenance treatment with pamiparib in combination with TMZ will be mandatory for all patients.

Dosing for this maintenance treatment should begin after the 4-week rest period (+ 7 days) to allow for recovery from RT treatment (please refer to [Appendix 1 Table 4](#)).

Arm C: Pamiparib (60 mg BID, administered continuously) in combination with increasing doses of TMZ ([Section 4.2.1](#)). TMZ will be administered on Days 1 to 21 of each 28-day cycle.

Approximately 60 patients may be enrolled in the 3 arms of the dose escalation phase. The actual sample size in this phase will depend on the number of dose escalation cohorts enrolled per arm.

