4.1.2. Dose Expansion Phase (Phase 2)

Once the safety, tolerability, PK, pharmacodynamic, and preliminary antitumor activity have been reviewed for the dose escalation cohorts of each of the arms, up to approximately 60 patients may be enrolled in expansion cohorts for each of the 3 arms at a dose level below or equal to the MTD or MAD for that arm. In Arm C, 2 expansion cohorts may be opened, one for unmethylated GBM and one for methylated GBM ([Section 4.3](#)).

Approximately 60 patients may be enrolled during the dose escalation phase, and in each of the 4 dose-expansion cohorts totalling 240 patients in the dose expansion phase, for an approximate total of 300 patients enrolled in the entire study.

Adverse events (AEs) during and after the treatment period with study drug(s) will be followed and documented as outlined in [Section 8.4](#) and [Section 10](#). AEs will be graded according to National Cancer Institute Common Toxicity Criteria for Adverse Events (NCI-CTCAE) v4.03.

To determine the PK properties of pamiparib, blood samples will be taken at various time points as outlined in [Section 8.5](#) and [Appendix 1](#). To determine pharmacodynamic effects of pamiparib, blood samples will be obtained coinciding with specific PK time points as outlined in [Section 8.5](#) and [Appendix 1](#).

Disease status will be assessed using Response Assessment in Neuro-Oncology (RANO) criteria ([Appendix 2](#)). Patients will undergo tumor assessments at screening and then every 8 weeks, or as clinically indicated.

In Arm B expansion phase of the study, maintenance treatment (pamiparib in combination with TMZ) will be mandatory for all patients. In Arm A expansion phase of the study, continuation of treatment (with pamiparib in combination with TMZ) will be at the discretion of the investigator after discussion with the Medical Monitor.

Following completion of RT, all patients in Arms A and B who continue on pamiparib in combination with TMZ should follow the schedule of assessments for maintenance treatment ([Appendix 1 Table 4](#)).

Patients in Arms A and B who have completed all study treatments per protocol and do not continue on pamiparib in combination with TMZ (maintenance) should have their EOT visit at the end of the Rest Phase, 28 days after RT was completed, unless they do not complete the full study treatment; in such a case, they should have the end-of-treatment (EOT) visit within 7 days of stopping all study treatment.

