4.2. Details of Dose-Escalation Stage

4.2.1. Starting Dose and Dose-Escalation Approach

Arm A

RT will be administered QD × 5 days/week for 6 to 7 weeks with 1.8 or 2 Gy/fraction for a total target dose of between 58 Gy and 64 Gy.

The starting dose for pamiparib will be the 60 mg PO BID based on the rationale outlined in [Sections 1.3](#) and [1.4](#). In Cohort 1, exposure to pamiparib will be limited to the first 2 weeks of RT. In Cohorts 2 and 3, pamiparib will be given for the first 4 and 6 weeks of RT, respectively. If 2, 4, or 6 weeks of combination treatment exceeds the MTD, alternative regimens for pamiparib may be explored after discussions with all investigators based on which regimen exceeded the MTD and

what toxicities were observed. For example, if 2 weeks of pamiparib are not tolerated, a schedule of 1 week on, 1 week off, or 1 week on and 3 weeks off may be explored. Depending on data available at that time, a lower dose level of pamiparib may also be explored.

Arm B

The opening of Arm B will depend on the safety of the Arm A combination, and Arm B may be enrolled at the initial dose and schedule of pamiparib found to be safe and tolerable in Arm A. RT will be administered as for Arm A.

The first dose level of TMZ will be lower than or equal to a dose that has been determined to be safe and tolerable in Arm C, and dose escalation will proceed as described for Arm C. The time period of TMZ administration may be the same or shorter than that for pamiparib administration. Similar to Arms A and C, alternative regimens may be explored with adjustments of dose and/or schedule as outlined for Arms A and C.

Arm C

Since TMZ is given as a DNA-damaging sensitizer for pamiparib and to simplify TMZ dosing, flat-dosing will be used for TMZ. The first dose level of 40 mg QD corresponds to 23 mg/m^2 assuming an average body surface area of 1.73 m^2 . Subsequent dose levels of 80 mg and 120 mg correspond to 46 mg/m^2 and 69 mg/m^2 , respectively. Additional higher dose levels may be explored, and the TMZ dose will not be increased by more than 50% each time. TMZ will be given on Days 1 to 21 of each 28-day cycle based on data and rationale discussed in [Sections 1.2, 1.3, and 1.4](#).

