Following the same rationale for pamiparib dosing as for Arms A and B, all patients will receive pamiparib of 60 mg PO BID continuously. If the MTD is exceeded for a combination regimen that is considered inadequate for further exploration based on all data available at that time, alternative regimens may be explored, such as a lower dose of pamiparib, a lower dose of TMZ, and/or alternative dosing schedules for either drug.

Depending on emerging safety data from this and other pamiparib Phase 1 studies, the pamiparib regimen may be switched to QD for one or more of the 3 arms at any time during or after dose escalation. The QD dose of pamiparib may be escalated according to the dose escalation rules in [Section 4.2.2](#) of the protocol.

Once Arm C dose escalation identifies the RP2D for the combination, that combination regimen may be applied in Phase 2 Arm A and B patients (see [Section 4.3](#)). Additionally, data emerging from other ongoing studies with pamiparib may be used to determine the combination regimen.

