7.1.2.3. Dosage and Administration

Temozolomide will be administered PO QD, preferably during the same time frame each day (ie always in the morning or always in the evening). The daily dose and schedule will be determined by arm and stage of study as outlined in [Section 4.2.1](#).

On days with PK assessments, TMZ should be administered in the clinic.

Patients will be instructed to swallow the capsules whole, in rapid succession, with water.

A dose of TMZ should be skipped if it is not taken within 2 hours of the scheduled time. An extra dose of TMZ should not be taken to make up for a missed dose. If vomiting occurs during the course of treatment, no re-dosing of the patient is allowed before the next scheduled dose.

Antiemetic prophylaxis is usually not required for TMZ. However, prophylaxis with a 5-HT₃ antagonist is recommended prior to administration of the first few TMZ doses and should be administered orally 30 to 60 minutes before TMZ treatment. Most patients report optimal nausea control with the use of a 5-HT₃ antagonist. If optimal nausea control cannot be achieved, any alternative dosing schedule, such as TMZ administration at night, should be discussed with the medical monitor before implementation.

For patients receiving TMZ (Arms B & C), *Pneumocystis jirovecii* pneumonia prophylaxis is required as outlined in [Section 7.2.2](#).

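### Arm A patients may take temozolomide in maintenance, but Pneumocystis prophylaxis is mandatory only in Arms B and C

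*Protocol*

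**What the plan says.** **Prophylaxis.** Protocol Section 7.2.2 gives two situations of high risk: TMZ 75 mg/m² given with radiotherapy (RT), and dose-dense TMZ ("dose-dense TMZ regimens especially in combination with chronic use of corticosteroids have a high risk for developing" this pneumonia). It then sets the requirement by arm: "For that reason, all patients in Arms B and C are required to receive" prophylaxis. Section 7.1.2.3 repeats the rule with the same limit: "For patients receiving TMZ (Arms B & C").

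**TMZ in Arm A.** Section 4.1.1 states that after RT "patients in the Arm A escalation and expansion and patients in Arm B escalation phases of the study may continue to receive pamiparib" together with TMZ. Section 4.1.2 leaves the same choice in the Phase 2 cohort to the investigator, once the medical monitor has been consulted: "In Arm A expansion phase of the study, continuation of treatment (with pamiparib in combination with TMZ) will be at the discretion". Appendix Table 4 is the maintenance schedule for both Arms A and B. Its footnote l caps TMZ at a dose found tolerable in Arm C. SAP Section 3.1.2 includes this maintenance in the Arm A Phase 2 objective.

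**Regimen.** Section 4.2.1 says of the Arm C combination, once its recommended dose is known, "that combination regimen may be applied in Phase 2 Arm A and B patients". For Arm C itself, "TMZ will be given on Days 1 to 21 of each 28-day cycle".

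**The concern.** The requirement is written by arm label, but its rationale is exposure to TMZ. Under the current protocol the labels no longer match the exposure: Section 7.1.2.3 in effect treats Arm A as TMZ-free, which holds only during RT. Two patients on the same two drugs could then be handled differently, with prophylaxis mandatory in Arm C and optional in Arm A maintenance. No reason for exempting Arm A is given.

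The same labels cause a smaller gap in Section 12.2.3. Advice on sperm cryoconservation is confined to men in Arms B and C, although the stated reason is possible infertility from TMZ. A minor consistency point is that exclusion 15 (hypersensitivity to TMZ components or dacarbazine) does not apply to Arm A, and the re-screening footnote of Appendix Table 4 adds no TMZ check. This will rarely matter, since inclusion 12 admits only patients with no prior treatment except surgery.

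**Working it through.** There is no figure in the plan to reproduce. The check sets the sections side by side and then bounds the size.

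**1. Is TMZ allowed in Arm A?** Yes: Sections 4.1.1 and 4.1.2, the Appendix Table 1 footnote on end of treatment, and Appendix Table 4.

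**2. Is prophylaxis required there?** No. Sections 7.1.2.3 and 7.2.2 name only Arms B and C. Neither Appendix Table 4 nor its footnotes mention prophylaxis, and nothing elsewhere extends it. Section 7.2.1 permits it as supportive care.

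**3. Does the protocol's own reason reach Arm A?**
- TMZ given with RT: no. Arm A has no TMZ during RT.
- Dose-dense TMZ: yes, if the Arm C schedule is used. That schedule gives TMZ on 21/28 = 75% of days. Section 4.2.1 allows it for Phase 2 Arm A patients but does not require it, and Appendix Table 4 states no dosing days.
- Indirect evidence on schedule: as extracted, Appendix Table 4 marks TMZ at the Day 15 visits of Cycles 1 and 2. Appendix Table 3 (Arm C) marks it at Days 1, 8 and 15 of Cycle 1 and leaves Day 22 blank, so the marks appear to follow dosing days. A Day 15 mark fits Days 1 to 21, not Days 1 to 5.
- Corticosteroids: inclusion 6 lets patients in every arm enter on dexamethasone up to 4 mg twice daily, and Section 7.2.1 permits glucocorticoids on study.

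**4. How many patients?** SAP Section 5 gives 40 in the Arm A expansion and 46 in Phase 1b across all arms. The ceiling is 40 + (Arm A share of 46), which is below 40 + 46 = 86. The Phase 1b split and the number who started maintenance are not given.

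**5. How large is the risk?** Section 1.2.4.1 reports, for 75 mg/m² on 21 of 28 days, Grade 3 or 4 lymphopenia in 24% to 53%. It also cites Grade 4 lymphopenia in 47% in one study of recurrent anaplastic astrocytoma or oligoastrocytoma, and says Grade 4 may raise the risk of opportunistic infection. The Arm A maintenance dose is not stated. Assuming one of the three listed Arm C levels, with the protocol's 1.73 m² body surface area:

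| TMZ dose | Equivalent | Relative to 75 mg/m² |
|---|---|---|
| 40 mg | 23 mg/m² | 23/75 = 31% |
| 80 mg | 46 mg/m² | 46/75 = 61% |
| 120 mg | 69 mg/m² | 69/75 = 92% |

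The background rates may therefore overstate the risk at the lower doses. The same section cites a large dose-dense trial with 12% Grade 3 or 4 lymphopenia and no significant opportunistic infections.

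**The case against.** The best counterargument accepts the mismatch in labels and disputes its importance.

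- **The dose-dense link is inferred.** Section 4.2.1 is permissive, refers to Phase 2 only, and lets Arm C itself move to other schedules. The Day 15 marks come from an extracted table. This stands: the 21-of-28-day schedule is an assumption, and it is weaker for Arm A escalation patients.
- **The lymphopenia rates come from other settings and higher doses.** This also stands. The 47% comes from a different, recurrent tumor population, and every listed Arm C dose is below 75 mg/m². But the protocol made prophylaxis mandatory in Arm C at those same doses.
- **Other safeguards exist.** Starting maintenance in Arm A requires investigator judgment and a discussion with the medical monitor. Prophylaxis is permitted. Maintenance hematology includes lymphocyte counts on Days 1 and 15, with Day 22 added under the TMZ prescribing information. These lower the risk, but monitoring is not prophylaxis, and the measure remains optional in Arm A.
- **The arm labels may be shorthand from the RT phase.** Possibly, and Section 7.1.2.3 does begin by referring to TMZ recipients. Its parenthesis and Section 7.2.2 nevertheless limit the rule to two arms.
- **It may be too late.** The SAP reports enrollment as complete at 116. Fertility advice before treatment would then come too late for these patients; prophylaxis still matters for anyone on maintenance.

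**Conclusion.** The concern holds and should be fixed. The scope of a mandatory safety measure omits a group that the protocol allows to take the same drug. That conclusion rests on the text alone. The further claim, that the dose-dense rationale applies to Arm A as much as to Arm C, assumes that maintenance follows the Days 1 to 21 schedule. Fewer than 86 patients could be affected, and only those who started maintenance; the fertility point concerns only the men among them. The documents do not allow an infection rate to be estimated. No endpoint, sample size or analysis is touched.

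**What to change.** - **Sections 7.1.2.3 and 7.2.2:** replace the arm labels with any patient receiving TMZ, including Arm A maintenance.
- **Section 12.2.3:** extend the sperm-cryoconservation advice, before first study treatment, to men in Arm A who may go on to TMZ maintenance. Change the consent form only if it does not already cover this.
- **Appendix Table 4, footnote a (minor):** confirm before maintenance that an Arm A patient has no known hypersensitivity to TMZ components or dacarbazine. Exclusion 16 carries the same arm limit and can be considered in the same edit.
- **If maintenance dosing has ended:** read prophylaxis use in Arm A from the concomitant-medication listing planned in SAP Section 6.3.4.

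The cost is a few words in four places, with no new visit, laboratory test or analysis.
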